7.5 Vital Signs

Vital signs (including systolic and diastolic blood pressure, heart rate, respiratory rate and temperature) will be determined at screening, on each visit day, as described in Tables 2, 3 and 4 and at follow up. Vital signs will be measured after the subject has been lying supine for at least 5 minutes.

7.6 ECG and Echocardiogram

A 12-lead ECG will be recorded for all subjects at screening, pre-dose and 30 minutes, 1, 2 and 4 hours (and 6, 8, 12 and 24 hours on Day 1) post-dose in Cycle 1, at the end of study dosing, and at follow up. For DC phase subjects only, ECG will be recorded predose and 4 hours post dose on each subsequent dosing day.

An ECG will be recorded after the subject has been lying supine for at least 5 minutes. The date and time the ECG was recorded, as well as the protocol and subject identification details should be recorded on the printout.

The following parameters will be recorded in the CRF: heart rate, PR, QRS, QT, QT_{cF} as well as any abnormality in rhythm or wave morphology.

In the DC phase only, subjects will undergo echocardiography during screening.

7.7 Body Weight, Height and BMI

Body weight will be measured at screening, Day 1 and 22 of Cycle 1, end of dosing or early discharge and follow up. For DC phase subjects only, body weight will be recorded once at the end of Cycles 2-3. Height will be measured at screening only. BMI will be calculated by the following formula:

BMI = Body weight $(kg)/(height)^2 (m^2)$

8. Pharmacodynamic (PD) & immune parameter sampling

Blood samples will be taken for PD and immune parameter assessment as described in Tables 2, 3 and 4. The tests will be performed by the Sponsor according to their laboratory standard operating procedures and may include some or all of the following.

Peripheral blood monocytes (PBMC production of IL-12p40, IL-12p70, IL-23, TNF α and IL-6 in response to stimulation with LPS/IFN γ ex vivo). Immune parameters (Serum IFN γ , IL-17, IL-6, TNF α and GM-CSF levels; PBMC expression of mRNA encoding IL-12p40, IL-12p35, IL-23p19, LT α , LT β , IFN γ , IL-17, GM-CSF, ROR γ t, and Tbet; PBMC production of IFN γ , IL-17, and GM-CSF in response to stimulation with anti-CD3 and anti-CD28 ex vivo).

9. Pharmacogenomic Analysis

Following specific written consent from the subjects, at least one aliquot of PBMC sample will be sent to [name], University of New South Wales for pharmacogenomic analysis. Samples will be stored for up to 25 years to permit investigation into genes of interest related to the immune system, thought to be associated with susceptibility to MS and other autoimmune diseases. The value of the research lies in the responsiveness or not to immune modulation with MIS416 may further validate some of the hypotheses being developed relating to immune system-related gene polymorphisms and susceptibility to disease.

10. Clinical Status Assessments

DC phase subjects will be assessed at the end of study for MS clinical status.

The appearance or reappearance of one or more clinical neurologic deficits, persisting for at least 48 hours following a period of relatively stable or improving status lasting at least 30 days, and/or loss of function reflected by an increase in EDSS, and/or the presence of new, expanding, or gadolinium-enhancing lesions (based on total T2 lesion burden) will be regarded as worsening clinical status.

The order in which these assessments are to be done will be as follows: MSFC, FSS, SF-36 and EDSS.

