4.5 Dose Confirmation Phase (up to total of 3 cycles)

The DC phase will not begin until the Sponsor has submitted to the Ethics Committee and regulatory authority the requisite sub-chronic nonclinical safety data, and received approval to proceed to 3 cycles of dosing.

In the DC phase, up to 15 subjects will be recruited at the RP2D. The Safety Team will have the responsibility of reviewing safety data from the DC phase of the trial and making recommendations regarding dose modifications. If a DC phase subject withdraws from dosing within the first 2 cycles for reasons unrelated to drug toxicity, the subject may be replaced at the discretion of the Safety Review Team.

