6.1 Screening (Days -28 to -2)

Subjects who are willing to participate in the study and who have signed a Consent Form will be screened for eligibility within 28 days of dosing.

Screening tests will include a record of medical history, a physical examination (excluding breast, genital or rectal examination, unless clinically indicated), vital signs, weight, height, ECG, safety laboratory tests (haematology, biochemistry, pregnancy test and/or FSH where applicable, hepatitis B, C and HIV serology, urinalysis) and drug of abuse screen. An Expanded Disability Status Scale will be completed (see Section 9.4). A cranial MRI scan will be performed during the screening period.

Subjects who meet all of the inclusion criteria and none of the exclusion criteria will be accepted onto the study.

Documentation of the subject's fulfillment of the entry criteria, whether eligible or not, is to be completed by the investigator.

6.2 Treatment Period (Cycle 1) – Day 1

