DC phase subjects will be admitted to the unit the morning of dosing for a brief physical examination (Day 1 only), weight (Day 1 and Day 22), ECG and vital signs. Any adverse events and concomitant medications taken since the last visit will be recorded and eligibility confirmed. An MSFC, FSS, and EDSS will be performed on Day 1 of each cycle, and the SF-36 will be performed at the end of Cycle 3 only. An ophthalmologic examination, to consist of visual acuity determination, biomicroscopy, and dilated fundoscopy, will be performed within a week of the end of Cycle 3. (EDSS will be repeated following neurological examination at any visit where indicated by a change in functional status).

A cranial MRI will be performed at the end of Cycle 3 (details to be provided in the companion Radiology Manual of Operations).

An indwelling intravenous cannula will be sited in a forearm. A pre-dose blood sample will be taken for safety samples (Days 8 and 22 in Cycles 2 and 3, and End of Dosing or Early Discontinuation where applicable). A pre-dose blood sample for PD and immune parameter analysis will be taken on Day 22 of each cycle.

Version 5

Study drug will be drawn up and administered at the scheduled time by a slow intravenous infusion over 10 minutes. Subjects will be closely monitored for changes in their health or physiological status. At any time during dosing, the infusion rate can be reduced or turned off in response to an adverse event occurring. Once the infusion is completed, the cannula will be flushed with 0.9% sodium chloride for injection. The cannula will stay *in situ* until discharge.

Subjects will be required to remain in bed for four hours post dose and then will be allowed to mobilise gently around the unit.

Vital signs will be repeated mid-way through the infusion (5 mins), 15 and 30 minutes, 2 and 4 hours post-dose. ECG will be repeated at 4 hours post-dose. Adverse event enquiry will be completed mid-way through the infusion, 15 and 30 minutes post dose and ongoing throughout the inpatient stay.

Meals, snacks and drinks will be provided throughout the day.

Subjects will be discharged mid afternoon but may remain in the unit for up to 24 hours at the discretion of the Investigator.

6.5 Treatment Period -End of Dosing (Day 29) or Early Discharge-(7 +1 days following last dose of drug)

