10.5 Cranial Magnetic Resonance Imaging (MRI)

Details of the protocol for cranial MRI scanning will be provided in the companion Operations Manual. MRI will be used to assess both safety and clinical status parameters.

11. Investigational Product

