14.5.3.6 Radiological Findings

Radiological (MRI) findings, including changes from baseline to each subsequent timepoint, will be summarized at each dose level for the following parameters:

- Gadolinium-enhancing lesions (number and volume)
- Total T2 lesion volume
- Brain parenchymal fraction

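### Section 10 judges new, expanding and gadolinium-enhancing MRI lesions by total T2 lesion burden, a net volume that cannot identify any of the three

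*Protocol*

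**What the plan says.** Protocol Section 10 (Clinical Status Assessments) gives three ways in which a dose-confirmation subject can be regarded as worse: a neurologic deficit of at least 48 hours, a rise in EDSS, or an MRI finding. They are linked by and/or: "and/or loss of function reflected by an increase in EDSS, and/or the presence of new, expanding, or gadolinium-enhancing lesions". The MRI limb is therefore sufficient by itself. Its basis is given in a parenthesis: "the presence of new, expanding, or gadolinium-enhancing lesions (based on total T2 lesion burden) will be regarded as worsening clinical status".

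Section 14.5.3.6 lists the MRI parameters to be summarised. The only T2 item is "Total T2 lesion volume". Enhancement is a separate item, "Gadolinium-enhancing lesions (number and volume"). The third is brain parenchymal fraction.

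Each subject has one scan before treatment (Section 6.1: "A cranial MRI scan will be performed during the screening period") and, in the dose-confirmation phase, one at the end of treatment or at early discharge (Sections 6.4 and 6.5.2, Table 4). Scanning details are left to companion manuals; Section 10.5 says: "Details of the protocol for cranial MRI scanning will be provided in the companion Operations Manual". The number of subjects concerned is small (Section 4.5: "In the DC phase, up to 15 subjects will be recruited at the RP2D").

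**The concern.** A total can say whether the overall volume went up or down. It cannot say whether a lesion is new, whether a particular lesion grew, or whether a lesion takes up contrast. If the parenthesis is applied as written, a subject with a new lesion can have a falling burden and not meet the criterion, while a subject with no new lesion can have a burden that rises through measurement error alone.

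Signs of activity on serial cranial MRI are part of the first secondary objective, and the synopsis places MRI findings among the clinical status tabulations. Section 2.3 gives ruling out an adverse effect of the drug on disease progression as one purpose of following these subjects. With at most 15 subjects and no control group, a few misclassified subjects change the picture, and no comparator would reveal it.

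**Working it through.** The protocol gives no cut-off, no measurement error for T2 volume and no expected rate of worsening, so there is no figure of its own to reproduce.

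**Step 1. Events against measures.**

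| Event named in Section 10 | Can total T2 burden show it? | Parameter in Section 14.5.3.6 that could |
|---|---|---|
| New T2 lesion | No, can be offset by shrinkage elsewhere | None |
| Expanding T2 lesion | No, same reason | None |
| Gadolinium-enhancing lesion | No, not a T2 volume measure | Enhancing lesion number and volume |

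**Step 2. Cancellation.** Illustrative volumes (assumed): baseline total 10.0 mL, one new lesion of 0.2 mL, older lesions shrink by 0.4 mL in all.

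10.0 + 0.2 − 0.4 = 9.8 mL

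The burden falls although a new lesion is present. This needs no assumption about measurement error. It also shows the limit of the example: the subject is missed altogether only if the new lesion does not enhance, EDSS does not rise and no lasting deficit appears, because any of these meets another part of the definition.

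**Step 3. Stable subjects called worse.** Assume no true change, two scans with independent normal errors, and per-scan coefficient of variation CV. The relative change then has SD √2 × CV, and for a threshold t on the relative rise:

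P(called worse) = 1 − Φ( t / (√2 × CV) )

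Example: t = 5%, CV = 5% gives 0.05 / 0.0707 = 0.707, and 1 − Φ(0.707) = 24%.

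| Threshold t | CV 1% | CV 2% | CV 5% | CV 10% |
|---|---|---|---|---|
| 0 (any rise) | 50% | 50% | 50% | 50% |
| 2% | 7.9% | 24% | 39% | 44% |
| 5% | <0.1% | 3.9% | 24% | 36% |
| 10% | <0.1% | <0.1% | 7.9% | 24% |
| 20% | <0.1% | <0.1% | 0.2% | 7.9% |

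The CVs and thresholds are assumptions; the protocol supplies neither. The first row is 50% by construction, because symmetric error is as likely to be positive as negative. With 15 stable subjects it would mean 15 × 0.5 = 7.5 called worse on average, and 5 or more with probability 94%. As soon as a threshold exists, the rate depends on it and on the CV.

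**The case against.** Four arguments weigh against the point.

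- **The text asks for the presence of lesions.** On a charitable reading, the parenthesis merely names the type of scan, and a new lesion counts whatever the total does. That may have been the intention, but the words make total burden the basis. They also attach it to enhancing lesions, where it makes no sense.
- **The rule may be in a manual or the SAP.** Neither is shown, and a minimum change or a lesion-level reading could be there. Its absence from the protocol is therefore not the fault alleged. However, the protocol refers to the manuals for the MRI protocol, whereas Section 10 itself states the basis for worsening. A manual that reads lesion by lesion would conflict with Section 10.
- **The numbers could be overstated.** A reader might infer that about half of stable subjects will be called worse. The protocol does not say that any rise above zero counts, so this does not follow. A reader might also infer a rate of missed worsening. Under an any-rise rule, with assumed burdens of 5–20 mL and CVs of 2–10%, a new 0.1 mL lesion without shrinkage elsewhere gives no net rise in 24–49% of cases. That range rests wholly on assumptions and ignores the enhancement, EDSS and deficit limbs, so it is not a rate of missed worsening for this trial.
- **Little depends on the composite.** This stands. Section 14.4.2 rules out formal testing. Section 14.5.4 summarises MSFC, FSS, SF-36, EDSS and exacerbations, not the composite. The parameter summaries in 14.5.3.6 are unaffected by the parenthesis, and no dose or stopping decision is tied to it.

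**Conclusion.** The point holds as a defect of definition. Section 10 bases three lesion-level events on a net volume that can identify none of them, and Section 14.5.3.6 does not supply the missing T2 count. This conclusion needs only the wording and the arithmetic of a sum.

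The resulting misclassification rate cannot be fixed from the protocol. The 50% figure applies only if any rise above zero counts, error is symmetric and there is no true change. The near 0% to 44% range applies to thresholds of 2–20% with assumed CVs of 1–10%. Neither is a prediction for this trial.

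The impact is modest: it falls on descriptive reporting of MRI and clinical status in up to 15 uncontrolled subjects. The wording should still be corrected, because it concerns a stated secondary objective and the repair is cheap.

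**What to change.** 1. In Section 10, delete the parenthesis on total T2 lesion burden.
2. Judge new or enlarging T2 lesions lesion by lesion, End of Dosing scan against Screening scan, with a minimum enlargement above measurement error fixed in advance. The minimum is essential. If any apparent growth counted, with symmetric and independent errors per lesion, a stable subject with k lesions would show at least one as enlarged with probability 1 − 0.5^k: 97% for 5 lesions and 99.9% for 10.
3. Keep gadolinium-enhancing lesions as a limb of their own, using the count already in Section 14.5.3.6.
4. Add the number of new or enlarging T2 lesions to Section 14.5.3.6.
5. Report total T2 volume only as a continuous change from baseline, not as a basis for calling a subject worse.
6. Bring the companion imaging manual into line with the revised wording.

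The cost is wording in two sections and the manual, plus a lesion-level comparison when the same two scans are read. No extra scan or visit is needed. The reader error of the lesion count cannot be estimated from the protocol.

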10.1 Multiple Sclerosis Functional Composite (MSFC)

Instructions for the administration and scoring of the Multiple Sclerosis Functional Composite^{19,20} are given in the MSFC Administration and Scoring Manual, National Multiple Sclerosis Society, 2001. It is presented in the companion Operations Manual.

The MSFC should be administered as close to the beginning of the study visit as possible and definitely before the patient does a distance walk. Every effort should be made to use the same testing room and designated area for the timed 8-meter walk at every visit. It is essential that the potential for distractions to be kept to a minimum and for all obstacles to be removed for the Timed 8-meter walk. All necessary materials should be assembled prior to the arrival of the subject.

10.2 Fatigue Severity Scale (FSS)

The Fatigue Severity Scale ⁽²²⁾ is a self-administered questionnaire to be completed by the subject. It is presented in the companion Operations Manual.

10.3 Short Form Health Survey SF-36

The Short Form Health Survey (SF-36)²⁴ is a self-administered questionnaire to be completed by the subject. It is presented in the companion Operations Manual.

10.4 Expanded Disability Status Scale (EDSS)

The Expanded Disability Status Scale^{21,24,25} will be completed by the physician following neurological examination. It is presented in the companion Operations Manual.

10.5 Cranial Magnetic Resonance Imaging (MRI)

Details of the protocol for cranial MRI scanning will be provided in the companion Operations Manual. MRI will be used to assess both safety and clinical status parameters.

11. Investigational Product

11.1 Dosage and Schedule of Test Drug

Four ascending dose levels of MIS416 (125, 250, 500 and 1000 μ g) are planned at this stage. Treatment is open label. Dosing will proceed as described in section 4.1.

11.2 Maximum Tolerated Dose

The MTD will be declared by the Safety Review Team, when at least 2 out of six subjects in a cohort experience a DLT. The MTD will be determined as the next lower dose in which <2 subjects experienced a DLT.

11.3 Formulation, Packaging and Labeling

MIS416 is a semi synthetic non toxic, non immunogenic, rod shaped microparticle (0.2 x 2.0 microns) composed of muramyl dipeptide repeats covalently attached to a poly amino acid backbone principally composed of lysine and glycine amino acid repeats. N-acetyl glucosamine is incorporated as an oxidizable carbohydrate for use in linking amino containing ligands. Single-stranded bacterial DNA is incorporated through amino linkages covalently attached to the poly amino backbone. Microparticle components are isolated from *Propionibacterium acnes*.

MIS416 is formulated in solution in 0.9% sodium chloride for injection at 0.2 mg/mL, packaged into 7 mL sterile glass vials and stored at 2° to 8° C.

11.4 Preparation and Administration of Test Drug

MIS416 will be administered intravenously into a peripheral vein. Administration will be as a slow intravenous infusion, over 10 minutes, using an infusion pump.

The required volume of drug will be drawn up from the vial and made up to 10 mL total volume with 0.9% sodium chloride for injection. The infusion must be made up no longer than 8 hours prior to administration. If the infusion is to be made up several hours prior to administration, then it should be stored in the refrigerator at 2° to 8° C and removed and brought up to room temperature just prior to administration.

Just prior to setting up the infusion, the syringe should be vigorously shaken for 30 seconds.

The infusion pump will be set at a rate of 1 mL/min, so that the dose is administered over 10 mins. Once the infusion is completed, the line will be flushed with 20 mL 0.9% sodium chloride for injection.

11.5 Accountability of Drug Supplies

The Sponsor will supply study drug to the investigational site. Drug supplies provided for this study will be manufactured under Good Manufacturing Practices, by the Sponsor, in Auckland, New Zealand, pursuant to a licence to manufacture medicines issued by Medsafe.

The study medication will be dispensed by the Site Investigator/Pharmacist.

Receipt of study drug, dispensing and administration logs will be kept by the pharmacist/investigator in the Investigator/Pharmacy files. At the end of the study, study drug will be reconciled and a copy of the record given to the CRA/sponsor. Surplus supplies of study drug will be returned to the Sponsor.

11.6 Recall of Investigational Product

In case of recall of investigational product (decided by the regulatory authority or the sponsor), the investigators will immediately be informed by the sponsor. The investigator will urgently attend to the following:

- Stop administration of the product to the subjects.
- Inform the concerned subjects.
- Contact the General Practitioners of the affected subjects
- Terminate the study

The sponsor will arrange for the return of the recalled product, according to their standard operating procedures.

12. Safety Issues

12.1 Warnings and Precautions

No evidence available at the time of completion of this study protocol indicated any special warnings or precautions were appropriate, other than those listed in the Investigator's Brochure.

12.2 Adverse Events and Laboratory Abnormalities

12.2.1 Clinical Adverse Events

An Adverse Event is any untoward medical occurrence in a patient or clinical investigation subject administered a pharmaceutical product and which does not have to have a causal relationship with this treatment. An Adverse Event can therefore be

Version 5

any unfavourable and unintended sign, symptom, or disease temporally associated with the use of a medicinal product, whether or not considered related to the medicinal product. Pre-existing conditions that worsen during a study are to be reported as Adverse Events.

An adverse event is any adverse change from the subject's baseline condition, including any clinical or clinically significant laboratory test value abnormality that occurs during the course of the clinical study after the experimental drug has been utilized, whether the adverse event is considered related to the treatment or not.

12.2.2 Severity Assessment

All clinical Adverse Events (AEs) encountered during the study will be reported on the AE page of the CRF. Intensity of the AEs will be classified in accordance with Guidance for Industry Toxicity Grading Scale for Healthy Adult and Adolescent Volunteers Enrolled in Preventative Vaccine Clinical Trials (issued by US DHHS September 2007) ("preferred term") and modified to include a systemic line item for rigors/chills.

12.2.3 Laboratory Test Abnormalities

Laboratory test results will appear on electronically produced laboratory reports submitted directly from the central laboratory and be recorded in the laboratory results pages of the CRF. Laboratory test value abnormalities as such should not be reported on the AE page of the CRF as AEs unless they result in a clinically relevant condition.

12.2.4 Serious Adverse Events (Immediately Reportable to Sponsor)

The definitions and reporting requirements of ICH Guidelines for Clinical Safety Data Management, Definitions and Standards for Expedited Reporting, Topic E2, will be adhered to.

An Adverse Event is regarded as serious if it is one of the following:

- Fatal
- Life-threatening
- Results in persistent or significant disability/incapacity
- Requires inpatient hospitalisation or prolongs hospitalisation
- Is a congenital anomaly/birth defect
- Clinically significant, requiring medical or surgical intervention to avoid one of the above.

Any AE that is serious, occurring during the course of the study and within 28 days of the end of the study, irrespective of the treatment received by the subject, and whether drug-related or not, must be reported to the Sponsor's Medical Monitor or designee,

Version 5

within 24 hours of the site becoming aware of it (expedited reporting). Reporting to the Sponsor must be made irrespective of the extent of the available AE information. Additional follow up information relating to the serious AE must be reported in a similarly expedited manner once it is available.

In addition, the investigator may be requested by the Sponsor or designee to obtain specific additional follow-up information in an expedited manner. This information may be more detailed than that captured on the AE CRF. In general, this will include a description of the AE in sufficient detail to allow for a complete medical assessment of the case and independent determination of possible causality. In the case of a subject death, a summary of post-mortem examination findings must be submitted as soon as possible to the Sponsor.

If a serious AE occurs, the following personnel are to be notified by fax within 24 hours of awareness of the event by the investigator:

[name], Medical Monitor:

| Fax | [contact] |
|-------|------------------------------------|
| Tel | [contact] or [contact] |
| Email | [contact] |

